	[name]
	[name]
Chudu labarataria	Leukocyte Adhesion Laboratory
Study laboratories	UnivProf. Dr. med. [name]
	Department of Anesthesiology, Intensive Care and Pain Medicine
	[name]
	[name]
Data Management	ESICM – [name] and [name]
	[contact]

CONFIDENTIAL

Date: 16.02.2017 Version: V1

II. Synopsis

Study-ID	07-Anlt-16				
Title of the trial	Biomarker-guided implementation of the KDIGO guidelines to reduce the occurrence of AKI after cardiac surgery– Prevention of AKI				
Acronym	PrevAKI – multicenter				
Responsible institution	Department of Anesthesiology, Intensive Care and Pain Medicine [name] [name]				
Medical condition	Elective cardiac surgery with extracorporeal circulation				
Trial type	Multicenter, prospective, randomized controlled, parallel group, clinical trial				
Objective(s)	Acute kidney injury (AKI) is a well-recognized complication after cardiac surgery with cardiopulmonary bypass (CPB) with an important impact on short- and long-term morbidity and mortality. CPB is employed in most cardiac surgical procedures. Despite numerous clinical trials testing different pharmacological treatments, a mean to prevent cardiac surgery-associated AKI (CSA-AKI) remains elusive. In 2012, the Kidney Disease: Improving Global Outcomes (KDIGO) workgroup published the KDIGO guidelines which recommend the implementation of a bundle of supportive measures to prevent AKI in patients with increased risk (discontinue all nephrotoxic agents when possible, discontinue angiotensin converting enzyme inhibitors(ACEi) and angiotensin receptor blockers (ARB) in the perioperative period to avoid severe hypotension, optimizing volume status and hemodynamic parameters, consider functional hemodynamic monitoring, close monitoring of serum creatinine and urine output, avoid hyperglycemia, consider alternatives to radiocontrast procedures). However, it is not clear whether this approach can prevent the occurrence of AKI in patients undergoing cardiac surgery. Moreover, it is not known how exactly to determinehigh risk. We hypothesize that the implementation of the KDIGO guidelines in highrisk cardiac surgery patients as identified by AKI biomarkers reduces the development of AKI.				

CONFIDENTIAL

Date: 16.02.2017 Version: V1

Intervention

Patients at high risk of AKI will be identified by measuring NC [TIMP-2]*[IGFBP7] (NephroCheck® Test) 4h after CPB. Patients with NC ≥ 0.3 will be randomized.

Validation group:

Implementation of the KDIGO guidelines:

Optimizing volume status and hemodynamic parameters (according to a hemodynamic algorithm, see **Figure 1.Hemodynamic** algorithm (validation arm), page 23), functional hemodynamic monitoring, discontinuation of all nephrotoxic agents when possible, discontinuation of angiotensin converting enzyme inhibitors(ACEi) and angiotensin receptor blockers (ARB) in the perioperative period to avoid severe hypotension, consideration of alternatives to radiocontrast agents, close monitoring of serum creatinine and urinary output, avoidance of hyperglycemia.

Control group:

The patients will receive standard of care. In these patients, cardiac output will be measured (e.g. by echocardiography, at initiation and then every 3h up to 12h) but the treating physician will not be informed about the values.

Key inclusion and exclusion criteria

Inclusion criteria:

- 1. Adult patients undergoing cardiac surgery with CPB
- 2. [TIMP-2]*[IGFBP7] ≥ 0.3 4h after CPB
- 3. Age between 18-90 years
- 4. Written informed consent

Exclusion criteria:

- Preexisting AKI
- 2. Patients with cardiac assist devices (ECMO, LVAD, RVAD, IABP)
- 3. Pregnancy
- 4. Known (Glomerulo-) Nephritis, interstitial nephritis or vasculitis
- 5. CKD with eGFR< 30 ml/min
- 6. Dialysis dependent CKD
- 7. Prior kidney transplant within the last 12 months
- 8. Participation in another intervention trial in the past 3 months
- Persons with any kind of dependency on the investigator or employed by the institution responsible or investigator
- 10. Persons held in an institution by legal or official order

Primary trial objective

To investigate the adherence to the trial protocol in a multi-center

CONFIDENTIAL

Date: 16.02.2017 Version: V1

	multinational setting as a pilot project for a large randomized controlled					
	trial (feasibility trial). Primary outcome: KDIGO recommendations fulfilled					
	at all time					
Study endpoints	Primary endpoint:					
	Compliance rate (proportion of patients who are treated according to the trial protocol): KDIGO recommendations fulfilled at all time					
	Secondary endpoints:					
	Occurrence of AKI according to the KDIGO guidelines within 72 hours after cardiac surgery					
	Moderate and severe AKI (according to the KDIGO guidelines)					
	Severity of AKI (according to the KDIGO guidelines)					
	 Renal recovery at days 30, 60 and 90 (renal recovery is defined as serum creatinine levels < 0.5 mg/dl higher than baseline serum creatinine) 					
	30-day, 60-day and 90-day mortality					
	Length of ICU stay					
	Length of hospital stay					
	Need and duration of renal replacement therapy					
	• RRT at days 30, 60, 90					
	 MAKE₃₀, MAKE₆₀ and MAKE₉₀ (major adverse kidney events consisting of mortality, dialysis dependency, persistent renal dysfunction (defined as serum creatinine ≥ 2x compared to baseline value) 					
	Determination of different biomarkers					
	 Assessment of safety: complications in particular those related to the implementation of the KDIGO guidelines will be 					
	documented. No side effects have been reported.					
Number of subjects	To be assessed for eligibility: n=1000					
	To be allocated to the trial: n=310					
	To be analyzed: n=280 (140/ treatment arm)					
Time plan	First patient first visit (FPFV): 01/06/2017					
	Last patients first visit (LPFV): 31/05/2018					
	Last patient last visit (LPLV): 01/08/2018					
	Final study report: 01/11/2018					
	7 mai stady roport. 01/11/2010					

CONFIDENTIAL

Date: 16.02.2017 Version: V1

Statistics	Power analysis
	The required sample size is n=280 patients in total. This sample size is
	determined as follows:
	Patients will be randomized in a 1:1 ratio to one of the two treatment
	arms (intervention versus control). Randomization serves to estimate the
	incidence of AKI as secondary outcome to generate pre-information in
	terms of a pilot study for an upcoming confirmatory trial.
	The primary endpoint of the PrevAKI-multicenter trial is the compliance
	rate (Primary outcome: KDIGO recommendations fulfilled at all time), i.e.
	the proportion of patients who are treated according to the trial protocol.
	In order to estimate the compliance rate, the two treatment groups will
	be pooled together. In the primary analysis the compliance rate across
	all study patients will be estimated along with a two-sided 95%
	confidence interval (CI).
	As the compliance rate cannot be quantified in advance, we pursue a
	worst case approach and assume a compliance rate of 50%. In this case
	the CI has maximal width. Based on this assumption, with a sample size
	of n=280 patients the calculated 95% CI according to Clopper-Pearson
	(Fleiss 2003) ranges from 44% to 56%. Therefore, in case of any
	observed compliance rate apart from the worst-case scenario, the 95%
	CI is never wider than 56%-44%=12%. This corresponds to an
	estimation of the compliance rate with a precision of plus/minus 6%.
Trial Registration	The trial will be registered in a public register in accordance with the
	recommendations of the ICMJE.

CONFIDENTIAL

Date: 16.02.2017 Version: V1

III. Abbreviations

Abbreviation Meaning

ACEi Angiotensin converting enzyme inhibitor

AKI Acute kidney injury

AKIN Acute Kidney Injury Network

ALI Acute lung injury

APACHE II Acute Physiology and Chronic Health Evaluation II

ARB Angiotensin receptor blocker

ARDS Acute respiratory distress syndrome

BMI Body MassIndex
BUN Blood urea nitrogen

CK Creatine kinase

CKD Chronic kidney disease CK-MB Muscle-Brain type CK

CPB Cardiopulmonary bypass

CRF Case report form
CRP C-reactive protein

CSA-AKI Cardiac surgery-associated acute kidney injury

CVP Central venous pressure

ECMO Extracorporeal membrane oxygenation

eGFR Estimated glomerular filtration rate

ESRD End-stage renal disease

Hb Hemoglobin Hk Hematocrit

IABP Intra-aortic balloon pump

ICH International Conference on Harmonization of Technical Requirements for

Registration of Pharmaceuticals for Human Use

IGFBP7 Insulin-like growth factor-binding protein 7

KDIGO Kidney Disease: Improving Global Outcomes

LVAD Left ventricular assist device MAKE Major adverse kidney event

MAP Mean arterial pressure

PCI Principal coordinating investigator

PTT Partial thomboplastin time

(07-Anlt-16) 16.02.2017 Version: V1

Date:

RIFLE Risk, Injury, Failure, Loss classification

RRT Renal replacement therapy

RVAD Right ventricular assist device

SAPS II Simplified Acute Physiology Score

SOFA Score Sequential Organ Failure Assessment Score

TIMP-2 Tissue inhibitor of metalloproteinases-2

CONFIDENTIAL

Date: 16.02.2017 Version: V1

1 Objective and specific aims

Acute kidney injury (AKI) is a well-recognized complication after cardiac surgery with an important impact on short- and long-term morbidity and mortality. Cardiopulmonary bypass (CPB) is employed in most cardiac surgical procedures. Despite numerous clinical trials testingdifferentpharmacologicaltreatments, a mean to prevent cardiac-surgery associated AKI (CSA-AKI) remains elusive. In 2012, the Kidney Disease: Improving Global Outcomes (KDIGO) workgroup published the KDIGO guidelines which recommend to implement a bundle of supportive measures in patients at high risk for AKI to prevent the development of AKI (discontinuationofall nephrotoxic agents when possible, optimization of volume status and hemodynamic parameters, discontinuation of angiotensin converting enzyme inhibitors (ACEi) and angiotensin receptor blockers (ARB) in the perioperative period to avoid severe hypotension, consideration of functional hemodynamic monitoring, close monitoring of serum creatinine and urine output, avoidance of hyperglycemia, consideration of alternatives to radiocontrast procedures). However, there is no evidence thatthis bundle of supportive measures actually prevents AKI.

Primary efficacy endpoint:

The primary endpoint is the compliance rate (proportion of patients treated according to the trial protocol):KDIGO recommendations fulfilled at all time

Secondary endpoint(s):

Occurrence of AKI within the first 72 hours after cardiac surgery (AKI is defined according to the KDIGO guidelines(1)); moderate and severe AKI (according to the KDIGO classification); severity of AKI; renal recovery at days 30, 60 and 90 (renal recovery is defined as serum creatinine levels < 0.5 mg/dl higher than baseline serum creatinine); 30-day, 60-day and 90-day mortality; length of ICU stay; length of hospital stay;need and duration of RRT; RRT at days 30, 60 and 90; MAKE₃₀, MAKE₆₀ and MAKE₉₀ (major adverse kidney events consisting of mortality, dialysis dependency persistent renal dysfunction (defined as serum creatinine ≥ 2x compared to baseline value).

Assessment of safety:

No side effects are expected by implementing the KDIGO guidelines.

CONFIDENTIAL

Date: 16.02.2017 Version: V1

2 Background and significance

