4.1.1 Time plan

The study comprises three main periods:

- Intervention period (from inclusion and randomization to 12 h)
- Observation period (during hospitalization)
- Follow-up period on day 90 after patient enrolment.

End of the clinical trial

The last patient's last visit (LPLV) is defined as the end of the clinical trial.

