4.7 Efficacy and safety variables

4.7.1 Measurement of efficacy and safety variables

- 4.7.1.1 Primary target variable
 - Compliance rate (proportion of patients who are treated according to the trial protocol):
 KDIGO recommendations fulfilled at all time
- 4.7.1.2 Secondaryand other target variables
- Occurrence of AKI within the first 72 hours after cardiac surgery (AKI will be defined according to the KDIGO guidelines)
- Moderate and severe AKI within 72 hrs (according to the KDIGO guidelines)
- Severity of AKI within 72 hrs
- Renal recovery

Renal recovery at hospital discharge and at days 30, 60 and 90 will be defined asserum creatinine levels < 0.5 mg/dl higher than baseline.

- 30-day, 60.day and 90-day mortality
- Length of stay in intensive care unit and hospital

CONFIDENTIAL

Date: 16.02.2017 Version: V1

Information on ICU and hospital stays will be documented. From admission to ICU admission until follow-up (by phone) at day 90, the location of the patient within the hospital will be documented in the CRF. The following will be recorded for each patient

- Date and time of admission to ICU
- Date and time of discharge from ICU
- Date and time of discharge from hospital
- Need and duration of RRT during hospital stay
- RRT at days 30, 60 and 90
- MAKE₃₀, MAKE₆₀ and MAKE₉₀ (major adverse kidney events consisting of mortality, dialysis dependency persistent renal dysfunction (defined as serum creatinine ≥ 2x compared to baseline value)
- Determination of different biomarkers

Blood and urine samples for biomarkers will be collected at the time of randomization and 12 hrs later

 Assessment of complications related to the implementation of the KDIGO guidelines will be documented.

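### The synopsis dates the last patient's last visit 62 days after the last enrolment, about four weeks too early for the protocol's 90-day follow-up

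*Combined protocol and SAP*

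**What the plan says.** The time plan in the synopsis (section II) gives four dates:

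- "First patient first visit (FPFV): 01/06/2017"
- "Last patients first visit (LPFV): 31/05/2018"
- "Last patient last visit (LPLV): 01/08/2018"
- "Final study report: 01/11/2018"

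Section 4.1.1 lists the study periods, the last of which is "Follow-up period on day 90 after patient enrolment". It then adds: "The last patient's last visit (LPLV) is defined as the end of the clinical trial".

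The 90-day horizon recurs elsewhere. Section 4.7.1.2 describes "follow-up (by phone) at day 90", and the visit table in section 4.7.1.3 places the follow-up visit (T7) at days 30, 60 and 90. The secondary endpoints in the synopsis include "30-day, 60-day and 90-day mortality", together with renal recovery, RRT and MAKE at the same three time points. Sections 1, 4.7.1.2 and 6.1 repeat them.

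No section shortens follow-up for late enrollees, sets a common closing date, or plans data collection after LPLV.

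**The concern.** The synopsis dates and the follow-up schedule cannot both hold. If the last patient enters on 31/05/2018 and everyone is followed for 90 days, the last visit cannot be on 01/08/2018. Because LPLV is also the end of the trial, the conflict affects the trial's stated duration as well as one line of a timetable.

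What is at stake is the completeness of four day-90 secondary endpoints in the last patients enrolled: mortality, RRT, renal recovery and MAKE90. If a site or the coordinating team planned staff and contacts around 01/08/2018, those patients could miss their day-90 assessment. A missed serum creatinine, which renal recovery and MAKE90 need, may not be recoverable later. Section 6.3 gives no rule for incomplete day-90 follow-up. For categorical endpoints it names Fisher's exact and chi-squared tests, and it names no time-to-event method that could use partial follow-up.

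**Working it through.** **Inputs.** From the synopsis: first enrolment 01/06/2017, last enrolment (LPFV) 31/05/2018, LPLV 01/08/2018, report 01/11/2018, 310 patients allocated, 280 analysed. From section 4.1.1: follow-up to day 90, counted from enrolment. The entry 31/05/2018 shows that dates are day/month/year. Read month first, 01/08/2018 would be 8 January 2018, which precedes the last enrolment and is impossible.

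**1. Try to reproduce the stated LPLV.**

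| Rule | Result |
|---|---|
| LPFV + 30 days | 30/06/2018 |
| LPFV + 60 days | 30/07/2018 |
| LPFV + 90 days, enrolment as day 0 | 29/08/2018 |
| LPFV + 89 days, enrolment as day 1 | 28/08/2018 |
| Stated | 01/08/2018 |

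Neither 90-day convention gives the stated date. The nearest match is a follow-up of about 60 days.

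**2. Size of the gap.** From 31/05/2018 to 01/08/2018 is 30 (June) + 31 (July) + 1 = 62 days. The shortfall is 90 − 62 = 28 days, or 27 if enrolment counts as day 1.

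**3. Who would fall short if 01/08/2018 were a hard stop.** The last enrolment date that reaches day 90 in time is 01/08/2018 − 90 days = 03/05/2018. Patients enrolled from 04/05/2018 to 31/05/2018, a span of 28 days, would not reach it. Recruitment from 01/06/2017 to 31/05/2018 lasts 365 days, so the share is 28/365 = 7.7%.

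**4. Number of patients, assuming even accrual.** The documents do not state an accrual pattern, so this is an assumption.

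- Allocated: 310 × 28/365 = 23.8, about 24.
- Analysed: 280 × 28/365 = 21.5, about 21.
- With enrolment as day 1 (27 days): 310 × 27/365 = 22.9 and 280 × 27/365 = 20.7, about 23 and 21.

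Recruitment weighted towards the end raises these numbers. Recruitment that is front-loaded or finishes early lowers them, possibly to zero.

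**5. What is not affected.** Day 60 for the last patient is 30/07/2018, two days before the stated LPLV, so the day-30 and day-60 endpoints fit. Compliance and AKI within 72 hours are complete well before then. The sample size rests only on the precision of the compliance rate (section 6.2). The Clopper-Pearson interval for 140/280 is 43.99% to 56.01%, which agrees with the plan's 44% to 56%.

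**6. Room in the timetable.** From 29/08/2018 to 01/11/2018 is 64 days. From 01/08/2018 it is 92.

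**The case against.** The strongest reply is that nothing is actually cut off. Section 4.1.1 defines the end of the trial by an event, the last patient's last visit, and attaches no calendar date to it. The visit schedule applies to every patient without exception. If sites follow it, the last visit is the last patient's day-90 contact, no data are lost, and 01/08/2018 is a wrong forecast in a protocol dated before recruitment began. This stands. A reader might infer that day-90 data are missing by design, but the documents do not support that: no section tells sites to stop follow-up on 01/08/2018.

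A reader might also infer that the database would be locked before the day-90 outcomes are in. That is not supported either. Section 4.8 ties lock to completion and cleaning of the data and gives no date.

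Even under a hard stop the effect is limited. A calendar cut-off under concurrent 1:1 randomisation does not depend on arm, so the main cost is precision. With 280 − 21 = 259 patients, intervals widen by a factor of √(280/259) = 1.04, about 4%. Nor would every affected outcome be missing: a patient who dies before the cut-off has a known 90-day mortality and MAKE90 status.

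The reply does not remove the contradiction. The date is printed as LPLV, LPLV is the end of the trial, and no other section reconciles it with day 90.

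**Conclusion.** The point holds as an internal inconsistency. The stated LPLV is 28 days too early for the protocol's own follow-up (27 if enrolment is day 1), and the figure needs correcting.

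The consequence for data is conditional. Only if 01/08/2018 were enforced as the end of the trial would patients from the last 28 recruitment days lack complete day-90 follow-up. The estimate of about 24 of 310, or 21 of 280, rests further on even accrual. The exposure is confined to the four day-90 secondary endpoints. The design, sample size, primary analysis and visit schedule are untouched.

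**What to change.** Restate LPLV in the synopsis as no earlier than 29/08/2018 (LPFV + 90 days), plus whatever visit window the trial allows. Confirm that the report date of 01/11/2018 is still workable: it would follow LPLV by 64 days instead of 92, or fewer once a visit window is added.

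The cost is a trial end about four weeks later and less time between the last visit and the report. No change to recruitment is needed.

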2.1 Background

AKI is defined as an acute loss of renal function developing over a period of hours to days and represents a common complication in patients undergoing cardiac surgery(2). Depending on how it is defined, AKI occurs in up to 45% of patients after cardiac surgery, and approximately 1 to 2% require renal replacement therapy (RRT) (3-5). It may occur in patients with preoperative normal kidney function as well as in patients with chronic kidney disease (CKD)(6). Several clinical conditions e.g. sepsis, hypovolemia, extended surgical procedures (cardiac surgery with CPB) and the use of nephrotoxic agents can result in the development of AKI. Complications associated with AKI, such as electrolyte imbalances, fluid overload and uremia can lead to life-threatening conditions and worsen patients' outcome.

CPB is employed in most cardiac surgical procedures, and although the mechanisms are not fully understood, ensuing ischemic and inflammatory injuries to renal tubular epithelial cells have been implicated in the cause of AKI(7). Despite numerous clinical trials of pharmacologicaltreatments, a mean to prevent CSA-AKI has remained elusive.

2.2 Evidence

Independent of the underlying disease, AKI is associated with an increased morbidity and mortality, especially in patients undergoing cardiac surgery with CPB (8, 9). Numerous studies demonstrate that 1/3 of patients undergoing cardiac surgery suffer from AKI in the postoperative period(7). Although most of the patients develop only a mild AKI, mortality rates are 5 times higher compared to patients without the development of AKI in the postoperative period(10). Minimal elevations of serum creatinine of 0.3 mg/dl are associated with higher mortality rates. Furthermore, patients surviving severe AKI are at high risk for the development of CKD and end-stage renal disease (ESRD) leading to worse long term outcome and a tremendous economic burden for the health care system. These facts give treatment strategies for the prevention of AKI a high priority(11).

In 2012, the KDIGO group worked out some strategies for the prevention of AKI(12). These include the discontinuation of all nephrotoxic agents when possible, consideration of alternatives to radiocontrast agents, optimization of volume status and hemodynamic parameters, discontinuation of angiotensin converting enzyme inhibitors (ACEi) and angiotensin

CONFIDENTIAL

Date: 16.02.2017 Version: V1

receptor blockers (ARB) in the perioperative period to avoid severe hypotension, the consideration of a functional hemodynamic monitoring, close monitoring of serum creatinine and urinary output and the avoidance of hyperglycemia. Whether this bundle of supportive measures is effective to prevent AKI needs to be proven.

In theperioperative period several classes of nephrotoxins are used, including antibiotics (e.g. vancomycin(13) and aminoglycosides(14)) and intravenous contrast agents(15). A number of studies have shown that these nephrotoxic agents may lead to a deterioration of renal function and consequently to AKI (13-16).

ACEi and ARBs are used to treat hypertension. A lot of patients undergoing cardiac surgery are on ACEi or ARBs which may cause severe and prolonged hypotension during anesthesia. These hypotensive episodes may lead to a reduced renal perfusion. Walsh et al. performed a cohort study on 33.330 patients undergoing non-cardiac surgery and demonstrated that intraoperative hypotensive episodes of less than 5 minutes with a MAP < 55 mmHg were associated with a significantly increased AKI rate (17). These datasupport the recommendation to discontinue ACEi and ARBs in the perioperative period and to consider functional hemodynamic monitoring to prevent the development of AKI.

Close monitoring of the classic biomarkers serumcreatinine and urinary output are important to detect functional damage early. The recommendation to avoid hyperglycemia stems from the landmark study by Van den Berghe et al. who showed a significant reduction of AKI in patients receiving strict glucose control(18). However, there are several trials showing that strict glucose control might not only be associated with higher AKI incidence but also with higher mortality rates(19, 20).

The severity of AKI is determined byvarious classification systems (RIFLE, AKIN, KDIGO) based on the degree of reduction of urinary output and/or increase of serum creatinine compared to baseline(1, 21). Both "classic biomarkers" are not appropriate for the detection of kidney damage without a loss of function, because both are functional markers. Urinary output is influenced by the use of diuretics and fluid status (e.g. hypervolemia) and has a low specificity. Serum-creatinine elevations are not detectable until 50% of the glomerular filtration rate (GFR) is lost, showing that this parameter has a low sensitivity. However, the injury occurs at a much earlier timepoint. New biomarkers such as [TIMP-2]*[IGFBP7] are injury markers which indicate tubular injury before loss of kidney functionoccurs(22). We performed an observational trial demonstrating that urinary [TIMP-2]*[IGFBP7] levels 4h after cardiac surgery showed a good performance to predict AKIwithin the next 72h (NC 0.3: sensitivity 0.80, specificity 0.83, PPV

CONFIDENTIAL

Date: 16.02.2017 Version: V1

0.80, NPV 0.83)(23). In those patients with AKI, biomarker elevations were apparent two days before the increase of serum-creatinine.

Recently, we performed a single-center trial investigating the effect of the implementation of the KDIGO bundles to obtain preliminary data. We found a significant decrease in the occurrence of AKI within 72 hours in high risk patients (defined as TIMP-2*IGFBP7≥0.3) undergoing cardiac surgery (55.1% in the intervention versus 71.7% in the control group, p=0.004).

In this feasibility trial we will analyze the compliance rate to the trial protocol in a multicenter, multinational cohort in preparation for a large randomized controlled trial.

